2.3. Study Design

This study is a randomized, active-controlled study to evaluate the safety, tolerability, and immunogenicity of new bivalent and monovalent vaccines. The study duration for each participant will be approximately 6 months. The study vaccine candidates are divided into cohorts, which may be studied in a staggered or parallel manner, as required by the clinical plan. Refer to the Schema in Figure 1.

Based on review of safety or immunogenicity data of any study intervention group, at Pfizer's discretion, subsequent collection of blood samples from participants in that group may be halted and/or not analyzed, and study visits or other procedures may be discontinued.

An EDMC will review cumulative unblinded data throughout the study.

Figure 1. Schema

3. ENDPOINTS AND BASELINE VARIABLES: DEFINITIONS AND CONVENTIONS

3.1. Primary Endpoint(s)

3.1.1. Safety Endpoints

The primary safety endpoints for all analysis groups are as follows:

- Local reactions for up to 7 days after the study vaccination
- Systemic events for up to 7 days after the study vaccination
- AEs from vaccination through 1 month after the study vaccination
- SAEs from vaccination through 6 months after the study vaccination

3.1.1.1. Local Reactions

The local reactions assessed and reported in the e-diary are redness, swelling, and pain at the injection site, from Day 1 through Day 7 after the study vaccination, where Day 1 is the day of the study vaccination. The e-diary entries from the participant and unplanned clinical assessments within 7 days after vaccination will be the primary data sources for these events. In addition, any events recorded on the AE CRF that are considered local reactions within 7 days after vaccination will be consolidated with e-diary data and included in the reactogenicity report. This section describes derivations with details for the assessment of local reactions: presence, severity level, duration, and onset day.

Presence or Absence

For each local reaction and any local reaction on any day, Table 3 explains the algorithm to derive the presence of a reaction (yes or no) during the interval from Day 1 through Day 7, where Day 1 is the day of the study vaccination.

Table 3. Derived Variables for Presence of Each and Any Local Reaction Within 7 Days for the Study Vaccination

Variable	Yes (1)	No (0)
Presence of each local reaction on any day.	reaction as "yes" on any	Participant reports the reaction as "no" on all 7 days (Day 1 through Day 7) or as a combination of "no" and missing on all 7 days (Day 1 through Day 7).
Presence of any local reaction on any day.	reaction as "yes" on any	For all 3 local reactions, participant reports "no" on all 7 days (Day 1 through Day 7) or as a combination of "no" and missing on all 7 days (Day 1 through Day 7).

Note: Completely missing e-diary data will not be imputed. Participants with no e-diary data reported will not be included in the e-diary summaries.

Severity and Maximum Severity

Redness and swelling will be measured and recorded in measuring device units (range: 1 to 21) and then categorized during analysis as absent, mild, moderate, or severe based on the grading scale in Table 4. Measuring device units can be converted to centimeters according to the following formula: 1 measuring device unit = 0.5 cm. Pain at the injection site will be assessed by the participant as absent, mild, moderate, or severe according the grading scale in Table 4.

For events recorded in the AE CRF that are considered local reactions and consolidated with e-diary data, the severity will be based on the AE intensity grade recorded in the CRF.

	Mild (Grade 1)	Moderate (Grade 2)	Severe (Grade 3)	Potentially Life-Threatening (Grade 4) ^a
Pain at the injection site	Does not interfere with activity	Interferes with activity	Prevents daily activity	Emergency room visit or hospitalization for severe pain
Redness	>2.0 cm to 5.0 cm (5 to 10 measuring device units)	>5.0 cm to 10.0 cm (11 to 20 measuring device units)	>10 cm (≥21 measuring device units)	Necrosis or exfoliative dermatitis
Swelling	>2.0 cm to 5.0 cm (5 to 10 measuring device units)	>5.0 cm to 10.0 cm (11 to 20 measuring device units)	>10 cm (≥21 measuring device units)	Necrosis

Table 4. Local Reaction Grading Scale

If a Grade 3 local reaction is reported in the reactogenicity e-diary, a telephone contact should occur to ascertain further details and determine whether a site visit is clinically indicated. Only an investigator or medically qualified person is able to classify a participant's local reaction as Grade 4. If a participant experiences a confirmed Grade 4 local reaction, the investigator must immediately notify Pfizer.

For each local reaction reported after the study vaccination, the maximum severity grade will be derived for the e-diary collection period (Day 1 through Day 7, where Day 1 is the day of the study vaccination) as follows:

Maximum severity grade = highest grade (maximum severity) within 7 days after administration (Day 1 through Day 7) among severity grades reported for that local reaction.

If a local reaction is captured in more than 1 data source, eg, e-diary, unplanned assessment, and/or the AE CRF, the highest grade (maximum severity) across all sources will be used in the summary.

Duration (First to Last Day Reported)

The duration (days) of each local reaction will be calculated as the number of days from the start of the first reported reaction to the resolution of the last reported reaction, inclusive (last day of reaction – first day of reaction + 1). Resolution is defined as the last day on which the reaction is recorded in the e-diary if the reaction lasts 7 days or less, or the day the reaction ends if it persists beyond the end of the reactogenicity e-diary period following the study vaccination (the latter will be collected on the CRF). If there is no known date when

a. Only an investigator or medically qualified person is able to classify a reaction as Grade 4; therefore, a confirmed Grade 4 reaction should be reported as an AE in the CRF and assessed by the investigator using the AE intensity grading scale.

the reaction ended, then duration will be missing (unknown). Participants with no reported reaction have no duration.

Onset Day

The onset day of each local reaction will be derived. Onset day is defined as the first day of reporting any severity.

For the onset day of each local reaction, if participants report change in severity of the local reaction, only the first day of reporting that specific local reaction will be counted.

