8.3.4.2. Local Reactions

During the reactogenicity e-diary reporting period, participants or participants' parent(s)/legal guardian will be asked to assess redness, swelling, and pain at the injection site and to record the symptoms in the reactogenicity e-diary. If a local reaction persists beyond the end of the reactogenicity e-diary period following vaccination, the participant or participant's parent(s)/legal guardian will be requested to report that information. The investigator will enter this additional information in the CRF.

Redness and swelling will be measured and recorded in measuring device units (range: 1 to 21) and then categorized during analysis as absent, mild, moderate, or severe based on the grading scale in Table 5. Measuring device units can be converted to centimeters according to the following formula: 1 measuring device unit = 0.5 cm. Pain at

the injection site will be assessed by the participant as absent, mild, moderate, or severe according to the grading scale in Table 5.

If a Grade 3 local reaction is reported in the reactogenicity e-diary, a telephone contact should occur to ascertain further details and determine whether a site visit is clinically indicated. Only an investigator or medically qualified person is able to classify a participant's local reaction as Grade 4. If a participant experiences a confirmed Grade 4 local reaction, the investigator must immediately notify Pfizer. A Grade 4 reaction will be collected as an AE on the CRF. The event will be graded using the AE intensity grading scale (Section 10.3.3).

Table 5. Local Reaction Grading Scale

	Mild (Grade 1)	Moderate (Grade 2)	Severe (Grade 3)	Potentially Life-Threatening (Grade 4 ^a)
Pain at the injection site	Does not interfere with activity	Interferes with activity	Prevents daily activity	Emergency room visit or hospitalization for severe pain
Redness	>2.0 cm to 5.0 cm (5 to 10 measuring device units)	>5.0 cm to 10.0 cm (11 to 20 measuring device units)	>10 cm (≥21 measuring device units)	Necrosis or exfoliative dermatitis
Swelling	>2.0 cm to 5.0 cm (5 to 10 measuring device units)	>5.0 cm to 10.0 cm (11 to 20 measuring device units)	>10 cm (≥21 measuring device units)	Necrosis

a. Only an investigator or medically qualified person is able to classify a reaction as Grade 4; therefore, a confirmed Grade 4 reaction should be reported as an AE in the case report form.

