- The investigator will then record all relevant AE or SAE information in the CRF.
- It is **not** acceptable for the investigator to send photocopies of the participant's medical records to Pfizer Safety in lieu of completion of PSSA/the Vaccine SAE Report Form/AE or SAE CRF page.
- There may be instances when copies of medical records for certain cases are requested by Pfizer Safety. In this case, all participant identifiers, with the exception of the participant number, will be redacted on the copies of the medical records before submission to Pfizer Safety.
- The investigator will attempt to establish a diagnosis of the event based on signs, symptoms, and/or other clinical information. Whenever possible, the diagnosis (not the individual signs/symptoms) will be documented as the AE or SAE.

Assessment of Intensity

GRADE	If required on the AE page of the CRF, the investigator will use the adjectives MILD, MODERATE, SEVERE, or LIFE-THREATENING to describe the maximum intensity of the AE. For purposes of consistency, these intensity grades are defined as follows:	
1	MILD	Does not interfere with participant's usual function.
2	MODERATE	Interferes to some extent with participant's usual function.
3	SEVERE	Interferes significantly with participant's usual function.
4	LIFE-THREATENING	Life-threatening consequences; urgent intervention indicated.

An event is defined as "serious" when it meets at least 1 of the predefined outcomes as described in the definition of an SAE, NOT when it is rated as severe.

Assessment of Causality

- The investigator is obligated to assess the relationship between study intervention and each occurrence of each AE or SAE. The investigator will use clinical judgment to determine the relationship.
- A "reasonable possibility" of a relationship conveys that there are facts, evidence, and/or arguments to suggest a causal relationship, rather than a relationship cannot be ruled out.
- Alternative causes, such as underlying disease(s), concomitant therapy, and other risk factors, as well as the temporal relationship of the event to study intervention administration, will be considered and investigated.
- The investigator will also consult the IB and/or product information, for marketed products, in their assessment.
- For each AE or SAE, the investigator must document in the medical notes that they have reviewed the AE or SAE and have provided an assessment of causality.

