3.1.1.2. Systemic Events

The systemic events assessed and recorded in the e-diary are fatigue, headache, chills, vomiting, diarrhea, new or worsened muscle pain, and new or worsened joint pain within 7 days after the study vaccination. The e-diary entries from the participant and unplanned clinical assessments within 7 days after vaccination will be the primary data sources for these events. In addition, any events recorded on the AE CRF that are considered systemic events starting within 7 days after vaccination will be consolidated with e-diary data and included in the reactogenicity report. The derivations for systemic events will be handled similar to the way local reactions are handled for presence of event, severity level, duration, and onset day (see Section 3.1.1.1).

The symptoms will be assessed by the participant as absent, mild, moderate, or severe according to the grading scale in Table 5 and recorded in the e-diary. For events recorded in the AE CRF that are considered systemic events and consolidated with e-diary data, the severity will be based on the AE intensity grade recorded in the CRF.

If a Grade 3 systemic event is reported in the reactogenicity e-diary, a telephone contact should occur to ascertain further details and determine whether a site visit is clinically indicated. Only an investigator or medically qualified person is able to classify a participant's systemic event as Grade 4. If a participant experiences a confirmed Grade 4 systemic event, the investigator must immediately notify the sponsor.

Table 5. Systemic Event Grading Scale

	Mild (Grade 1)	Moderate (Grade 2)	Severe (Grade 3)	Potentially Life-Threatening (Grade 4)
Vomiting	1-2 times in 24 hours	>2 times in 24 hours	Requires IV hydration	Emergency room visit or hospitalization for hypotensive shock
Diarrhea	2 to 3 loose stools in 24 hours	4 to 5 loose stools in 24 hours	6 or more loose stools in 24 hours	Emergency room visit or hospitalization for severe diarrhea

Table 5. Systemic Event Grading Scale

	Mild (Grade 1)	Moderate (Grade 2)	Severe (Grade 3)	Potentially Life-Threatening (Grade 4)
Headache	Does not interfere with activity	Some interference with activity	Prevents daily routine activity	Emergency room visit or hospitalization for severe headache
Fatigue/tiredness	Does not interfere with activity	Some interference with activity	Prevents daily routine activity	Emergency room visit or hospitalization for severe fatigue

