If a fever of ≥39.0°C (≥102.1°F) is reported in the reactogenicity e-diary, a telephone contact should occur to ascertain further details and determine whether a site visit is clinically indicated. Only an investigator or medically qualified person is able to confirm a participant's fever as >40.0°C (>104.0°F). If a participant experiences a confirmed fever >40.0°C (>104.0°F), the investigator must immediately notify Pfizer. Fevers >40.0°C (>104.0°F) will be collected as an AE on the CRF and assessed by the investigator using the AE intensity grading scale (Protocol, Section 10.3.3). If a fever is reported in the AE CRF within 7 days after vaccination and no temperature was captured in the CRF, the fever will be included in the reactogenicity summary with "unknown" for temperature range.

Table 6. Scale for Fever

≥38.0-38.4°C (100.4-101.1°F)	
>38.4-38.9°C (101.2-102.0°F)	
>38.9-40.0°C (102.1-104.0°F)	
>40.0°C (>104.0°F)	

If a systemic event is captured in more than 1 data source, eg, e-diary, unplanned assessment, and/or the AE CRF, the highest grade (maximum severity) across all sources will be used in the summary.

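### Solicited reactions taken from the AE CRF are graded by AE intensity, so a confirmed Table 4/5 Grade 4 reaction can be tabulated as Grade 3 or lower, and CRF-only size- or count-graded reactions get a functional grade

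*SAP*

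**What the plan says.** SAP Section 3.1.1.1 provides that "any events recorded on the AE CRF that are considered local reactions within 7 days after vaccination will be consolidated with e-diary data". On grading, it says that for AE CRF events "considered local reactions and consolidated with e-diary data, the severity will be based on the AE intensity grade recorded in the CRF". Section 3.1.1.2 applies the same rule to AE CRF events "considered systemic events and consolidated with e-diary data, the severity will be based on the AE intensity grade recorded in the CRF". If a local reaction appears in more than one source (diary, unplanned assessment, AE CRF), "the highest grade (maximum severity) across all sources will be used in the summary"; Section 3.1.1.2 repeats this for systemic events.

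Protocol Section 8.3.4.2 states: "A Grade 4 reaction will be collected as an AE on the CRF. The event will be graded using the AE intensity grading scale", and refers to Section 10.3.3. Section 8.3.4.3 says the same for systemic events, and footnote a to SAP Table 4 agrees for local reactions. Protocol and SAP are therefore consistent with each other.

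The two scales differ at Grade 4. For injection-site pain, Table 4 requires "Emergency room visit or hospitalization for severe pain". Section 10.3.3 requires "Life-threatening consequences; urgent intervention indicated".

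Fever is handled differently. If a fever comes from the AE CRF and "no temperature was captured in the CRF, the fever will be included in the reactogenicity summary", its temperature range is shown as unknown.

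SAP Sections 6.1.1.1.1 and 6.1.1.2.1 report reactions by maximum severity and cumulatively across severity levels.

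**The concern.** Tables 4 and 5 grade by lesion size, episode count, need for IV hydration, effect on activity, or the level of care reached. The Section 10.3.3 scale grades by interference with usual function, up to life-threatening. Merging the two and taking the maximum gives the right answer only if the AE CRF grade means the same as the table grade.

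It does not at Grade 4. The reactions the plan itself defines as Grade 4 are sent to the AE CRF, and there they are regraded on a scale with a different top category. The severity rows of a primary safety endpoint may then understate the worst reactions. This matters most in Cohort 4, where protocol Section 4.2 describes the first clinical study of four of the candidates and each arm has 60 participants.

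**Working it through.** The plan gives no figure to reproduce, so the check sets the scales side by side and follows the stated rule.

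**Step 1. Scales** (SAP Tables 4 and 5; protocol Section 10.3.3)

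| Reaction | Table 4/5 basis | Table 4/5 Grade 4 | AE intensity basis |
|---|---|---|---|
| Pain | Effect on activity | Emergency care or admission | Function; Grade 4 is life-threatening |
| Redness | Size; Grade 3 above 10 cm | Necrosis or exfoliative dermatitis | Same |
| Swelling | Size; Grade 3 above 10 cm | Necrosis | Same |
| Headache, fatigue, chills, muscle or joint pain | Effect on activity | Emergency care or admission | Same |
| Diarrhea | Stool count | Emergency care or admission | Same |
| Vomiting | Count; Grade 3 is IV hydration | Emergency care or admission for hypotensive shock | Same |

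**Step 2. Rule.** Tabulated grade = max(diary grade, unplanned-assessment grade, AE intensity). Participants rate only up to severe, and only an investigator or medically qualified person can assign Grade 4. The diary therefore contributes at most 3.

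**Step 3. Confirmed Grade 4, with no Grade 4 from an unplanned assessment.** Diary {missing, 0, 1, 2, 3} × AE intensity {1, 2, 3, 4} gives 5 × 4 = 20 combinations. These are counts of possibilities, not probabilities.
- Tabulated as Grade 4: only if AE intensity is 4, so 5 of 20.
- Grade 3: AE intensity 3 with any diary value (5), plus AE intensity 1 or 2 with diary 3 (2), so 7 of 20.
- Grade 2: 5 of 20. Grade 1: 3 of 20.

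Example: an emergency room visit for severe headache, diary Grade 3, investigator rates the AE severe. Max(3, 3) = 3, although Table 5 makes it Grade 4. A fall below Grade 3 needs a diary grade that is missing or below 3 together with mild or moderate AE intensity.

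**Step 4. Redness or swelling graded by size.** With a diary size, {0, 1, 2, 3} × AE intensity {1, 2, 3} gives 12 combinations. The size grade stands in 6, is raised in 6 and is lowered in none. With no diary entry, AE intensity is the only grade unless an unplanned assessment supplies one.

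Example: an 11 cm redness that does not limit function and is rated mild. With a diary entry, max(3, 1) = 3. From the AE CRF alone it is 1. In the other direction, redness of 2.0 cm or less is below Table 4 mild but would count as at least mild from the AE CRF. Diarrhea counts, and vomiting counts or IV hydration, follow the same logic. CRF-only events are foreseen: protocol Section 8.3.4 sends an event missed in the diary and told to the site to the AE page.

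**Step 5. Weight of one event.** 1/60 = 1.7 percentage points in a Cohort 4 arm; 1/100 = 1.0 point in a Cohort 2 group.

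**The case against.** The strongest reply is that this is a deliberate convention on which protocol and SAP agree, in a descriptive safety analysis. The estimand is the percentage reporting each reaction, and severity is a breakdown of it. A confirmed Grade 4 is not lost from view: the sponsor is notified at once, the event is recorded as an AE, a hospitalization is an SAE and is listed, and an external committee monitors safety. All of that stands and limits the consequence. It does not make the severity row right.

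Three stronger readings are tempting, and the documents do not support them.

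- A reader might infer that redness and swelling always lose their size-based grade. They do not. Under the highest-grade rule a diary size grade is a minimum and is never lowered. The same holds for vomiting and diarrhea.
- A reader might infer that the Grade 4 row is practically out of reach. Unplanned clinical assessments are a primary data source under the SAP and enter the maximum. Protocol Section 8.10.6 allows telephone confirmation, but also requires a site visit unless a listed exception applies. Some Table 5 criteria, such as vomiting with hypotensive shock, would plausibly be rated AE intensity 4. The documents do not show whether the assessment form records a table grade.
- A reader might infer a general upward shift, because AE Grade 3 is worded more loosely than diary Grade 3. Protocol Section 8.3.4 says diary events generally need not be entered as AEs, so few events would carry both grades, and the error would be in the cautious direction.

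**Conclusion.** The point holds in two parts. First, a reaction confirmed as Grade 4 under Table 4 or 5 is tabulated as Grade 3 or lower whenever its AE intensity is below 4 and no unplanned assessment carries the Grade 4. Second, redness, swelling, vomiting and diarrhea known only from the AE CRF receive a functional grade in place of the size- or count-based one.

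The effect is on the by-severity rows; whether a reaction is counted as present is essentially unaffected. Its extent cannot be worked out from the documents. They give no event counts, and the CRF is not included, so it may already hold lesion size or a reactogenicity grade. The conclusion assumes that the stated grading rule is applied as written. It is an analysis choice worth correcting because it concerns the reporting of a primary safety endpoint and costs little to change.

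**What to change.** Amend SAP Sections 3.1.1.1 and 3.1.1.2:

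1. Tabulate any investigator-confirmed Table 4 or Table 5 Grade 4 reaction as Grade 4 in the reactogenicity tables, whatever its AE intensity. The notifications to the sponsor required by protocol Sections 8.3.4.2 and 8.3.4.3 already identify these events and can be reconciled with the AE data before analysis.
2. For redness, swelling, vomiting or diarrhea known only from the AE CRF, grade from the recorded size or count where there is one. Otherwise count the reaction as present with severity unknown, as the SAP already does for fever without a temperature.
3. Keep AE intensity for the AE tables.

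The cost is SAP wording and a little programming. The downside is that a few events move to an unknown row and the investigator's intensity rating for them appears only in the AE tables. A CRF field for reactogenicity grade, size or count would help from here on but is optional; it cannot recover what was not recorded in cohorts already completed.

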The investigator or designee must obtain stop dates from the participant or participant's parent(s)/legal guardian for any ongoing local reactions, systemic events, or use of antipyretic medication on the last day that the reactogenicity e-diary was completed. The stop dates should be documented in the source documents and the information entered in the CRF.

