6.1.1.1.2. Supplemental Analysis

To support the assessment of local reactions, the following endpoints (as defined in Section 3.1.1.1) will be summarized with the same analysis time point and analysis population as above, and appropriate analysis methodology and reporting results:

- Duration (days) of each local reaction after the study vaccination.
- Onset day of each local reaction after the study vaccination.

These continuous endpoints will be summarized by displaying n, mean, median, standard deviation, minimum, and maximum by group.

Figures:

Bar charts with the proportions of participants for each local reaction throughout 7 days after the study vaccination will be plotted by group. The bars will be divided into severity categories to highlight the proportions of participants by maximum severity.

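### The SAP's duration rule ignores the CRF stop date when the e-diary ends before Day 7 and the reaction stops by Day 7, and its two clauses overlap for reactions of 7 days or less that end after Day 7.

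*SAP*

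**What the plan says.** Duration is an inclusive day count: last day of the reaction, minus first day, plus 1 (SAP 3.1.1.1, Duration). The last day comes from one sentence with two clauses.

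- First clause: "Resolution is defined as the last day on which the reaction is recorded in the e-diary if the reaction lasts 7 days or less".
- Second clause: "or the day the reaction ends if it persists beyond the end of the reactogenicity e-diary period following the study vaccination", with the note that "the latter will be collected on the CRF".

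The same section fixes the e-diary collection period as Day 1 through Day 7. If no end date is known, duration is missing.

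Protocol 8.3.4 sets a different trigger for collecting stop dates. The site must obtain one "for any ongoing local reactions, systemic events, or use of antipyretic medication on the last day that the reactogenicity e-diary was completed" and enter it in the CRF. That last completed day can be any of Days 1 to 7.

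The rule also reaches systemic events (SAP 3.1.1.2) and, where applicable, antipyretic use (SAP 3.1.1.3). Duration is summarised by group under SAP 6.1.1.1.2 ("Duration (days) of each local reaction after the study vaccination") and SAP 6.1.1.2.2.

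**The concern.** The two documents use different conditions. The protocol asks whether the reaction was ongoing when the participant last completed the diary. The SAP's first clause asks how long the reaction lasted, and its second asks whether it went past Day 7. The conditions part company in two places.

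- **Diary stopped early, reaction over by Day 7.** The second clause is not triggered, so the reaction ends at its last diary entry even though a later stop date is on the CRF.
- **Reaction of 7 days or less that ends after Day 7.** Both clauses are satisfied and they give different answers.

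What is at stake is the accuracy and reproducibility of the duration tables. Where the first clause governs, the effect is always to shorten, and it falls on participants who stopped recording while still symptomatic. Two programmers could also derive different values from the same late-onset record.

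**Working it through.** The documents state no figure on this point, so there is nothing of theirs to reproduce. The check applies the rule as written.

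**Inputs.** s = onset day; L = last diary day on which the reaction is recorded; E = CRF stop day, with E later than L. The diary period ends on Day 7 (SAP 3.1.1.1).

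**Formulas.**
- Duration to the recorded stop: E − s + 1.
- First clause, applicable if E − s + 1 ≤ 7: gives L − s + 1.
- Second clause, applicable if E > 7: gives E − s + 1.

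| s | L | E | To CRF stop | First clause | Second clause | Reading |
|---|---|---|---|---|---|---|
| 2 | 3 | 6 | 5 | 2 | does not apply | too short by 3 |
| 2 | 4 | 6 | 5 | 3 | does not apply | too short by 2 |
| 1 | 3 | 7 | 7 | 3 | does not apply | too short by 4 |
| 5 | 7 | 10 | 6 | 3 | 6 | two answers |
| 3 | 4 | 9 | 7 | 2 | 7 | two answers |
| 1 | 7 | 10 | 10 | does not apply | 10 | correct |
| 1 | 3 | 9 | 9 | does not apply | 9 | correct |

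**Every combination** with s from 1 to 7, L from s to 7 and E from L + 1 to 14:
- Diary stopped before Day 7 (203 combinations): 56 meet the first clause only, 35 meet both, 112 meet the second only.
- Diary completed to Day 7 (49 combinations): none meets the first clause only, 21 meet both, 28 meet the second only.

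Definite shortening therefore occurs only after an early diary stop. The largest shortfall in that class is 6 days (s = 1, L = 1, E = 7: 1 day instead of 7). These are counts of possible records, not expected frequencies.

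**Illustrative frequency.** The documents give no diary-completion or duration data, so the following inputs are assumptions: onset probabilities 0.45, 0.35, 0.10, 0.04, 0.03, 0.02 and 0.01 for Days 1 to 7; geometric duration with mean 2 or 3 days; 5%, 10% or 20% of diaries ending uniformly on Days 1 to 6. The simulation used 400,000 reactions per scenario. Letting the second clause govern every reaction that ends after Day 7, early-stopped diaries shorten 0.7–4.4% of reactions, by 1.7–2.1 days each. The effect on the mean is:
- low end: 0.007 × 1.7 ≈ 0.012 day, about 0.6% of a mean of 2 days;
- high end: 0.044 × 2.1 ≈ 0.092 day, about 3% of a mean of 3 days.

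**The case against.** The best defence is that the sentence is a simple split: reactions over within the diary week use the diary, and those that outlast it use the CRF. That matches Protocol 8.3.4.2, which has persisting local reactions entered in the CRF. On this reading, onset Day 5 with stop Day 10 plainly outlasts the diary period and belongs to the second clause. This is a sensible reading and probably the intended one, but the text tests the reaction's length, so the overlap remains. It does nothing for the early-stopped diary, where the reaction does not outlast Day 7.

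It can also be said that preferring the diary is deliberate. The heading speaks of first to last day reported, and diary entries and unplanned assessments are the primary sources. Stop dates may be recalled at Visit 2 or at Visit 3, 28 to 35 days after vaccination, and missed diary days are assumed free of reactions (SAP 2.2). The recall point stands as a limitation. The rest does not justify the rule: it already accepts CRF end dates for longer reactions and sets unknown ends to missing, so it aims at actual resolution. SAP 3.1.1.1 says how sources are combined for maximum severity (highest grade across all sources) but gives no such precedence for duration.

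A reader might infer that every reaction ongoing when the diary stopped is cut short. The documents do not support that. A reaction that lasts more than 7 days and ends after Day 7 takes its CRF end date, whether or not the diary was complete.

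**Conclusion.** The point holds in two parts of different strength.

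1. **Wrong as written.** When the diary was last completed before Day 7 with the reaction ongoing, and the reaction ended by Day 7, the SAP does not use a stop date that the protocol requires. The duration is too short, by up to 6 days for a single record.
2. **Ambiguous, not a certain error.** When a reaction lasts 7 days or less but ends after Day 7, both clauses apply and no precedence is stated. It would be tempting to count all of these as truncated, which raises the illustrative share to 2.7–8.5% of reactions. That figure depends on the first clause winning the overlap, which the SAP does not say.

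The 0.7–4.4% range for part 1 rests wholly on assumed onset, duration and early-stop rates; the actual frequency is unknown. It also treats the CRF stop date as the actual end.

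The consequence is minor. It is confined to descriptive duration summaries for local reactions, systemic events and, where applicable, antipyretic use. Presence, maximum severity and all hypothesis tests are unaffected.

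**What to change.** In SAP 3.1.1.1, replace the resolution sentence and drop the condition on lasting 7 days or less. Suggested text:

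> For a reaction still present on the final day for which the e-diary was completed, whether or not that is Day 7, resolution is the CRF stop date. In all other cases, resolution is the latest day with the reaction entered in the e-diary.

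Add two clarifications:
- The assumption of no reactions on missing diary days does not override a CRF stop date when duration is derived.
- A reaction ongoing at the last completed diary day with no CRF stop date has missing duration, under the existing rule for unknown end dates.

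The change carries over to systemic events and antipyretic use through SAP 3.1.1.2 and 3.1.1.3.

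The cost is a few lines of SAP text and a small change to the derivation program. No new data are needed, because Protocol 8.3.4 already requires the stop dates. The drawbacks are small: some durations will rest on dates recalled at Visit 2 or 3, and a few will become missing.
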